6.1.2 Serious Adverse Event (SAE)

An SAE fulfils at least one of the following criteria:

- Is fatal – results in death (NOTE: death is an outcome, not an event)
- Is life-threatening
- Requires in-patient hospitalisation or prolongation of existing hospitalisation
- Results in persistent or significant disability/incapacity
- Is a congenital anomaly/birth defect
- Is otherwise considered medically significant by the Investigator

Serious adverse events will be reported to the Principal Investigator and the Sponsor (see [Section 6](#)) within 24 hours. The 24 hours emergency contact numbers are listed on page iii of this protocol.

Serious adverse events will also be reported to:

- Barts Health NHS Trust, School of Medicine and Dentistry, Joint Research Office.

- National Research Ethics Service (NRES) approved Research Ethics Committee (the responsibility of the investigator) as soon as possible, but in any case, within 72 hours.

All available information will be provided, referring to the Serious Adverse Event paragraph of the Reporting Adverse Events document ([Appendix 1](#)). The Investigator will complete the Serious Adverse Event Form by carefully following the relevant instructions ([Appendix 1](#)) and will fax it within 24 hours to the Sponsor.

The Investigator, and others responsible for subject care, should institute any supplementary investigations of serious adverse events based on their clinical judgment of the likely causative factors. This may include seeking further opinion from a specialist in the field of the adverse event.

The Sponsor may also request extra tests. Continuation of the trial will be contingent upon approval from an independent safety review Committee.

6.1.3 Non Serious Adverse Events

A non-serious adverse event is one, which does not meet any of the criteria listed in the Section 6.1.3 defining serious adverse events, which is otherwise judged by the Investigators as significant.

If a non-serious adverse event occurs, the Investigator will fill in one Adverse Event Form for each adverse event describing its complete evolution to the outcome. Therefore the assessment of severity, frequency and causality will be given at the event outcome. The completed Adverse Event Form will be sent to the Sponsor.

During a clinical study, an adverse event previously reported as a non-serious event may change becoming, upon the Investigator's clinical judgment, a serious adverse event (i.e. dramatic worsening with hospitalisation etc.). At this moment, the Investigator will follow directions for reporting a serious adverse event.

6.2 INVESTIGATORS ASSESSMENT

6.2.1 Seriousness

The Chief/Principal Investigator responsible for the care of the patient, or in his absence an authorised medic within the research team, is responsible for assessing whether the event is serious according to the definitions given in [Section 6.1.2](#).

6.2.2 Causality

The Investigator must assess the causality of all serious adverse events in relation to the trial treatment according to the definition given

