6.0 PHARMACOVIGILANCE

Not applicable to current protocol has no treatment or therapy is a consequence of planned actions.

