6.1 GENERAL DEFINITIONS

6.1.1 Adverse Event (AE)

During any clinical study, onset of Adverse Events may occur. An AE is defined as any untoward medical occurrence in a patient or clinical investigation subject administered a pharmaceutical product or intervention and that does not necessarily have a causal relationship with this treatment (where 'treatment' includes also all investigational agents such as comparative agents and placebo). An adverse event can therefore be any unfavourable and unintended sign, symptom, or disease.

All adverse events encountered during the clinical study are to be reported on the Adverse Event Forms contained in the Case Report Form (CRF). For each adverse event which occurs during the clinical study the Principal Investigator will give a judgment on its severity and make a causality assessment of the treatment using one of the four given definitions: certainly related, probably related, possibly related and definitely unrelated. Moreover, the Principal Investigator will indicate the action to be taken for the adverse event that has occurred and its outcome.

In the case of an adverse event, the trained medical personnel will act with appropriate diagnostic and therapeutic measures until the subject has recovered. Adverse events will be classified as 'serious' and 'non serious'. All this information will be recorded for each adverse event on the Adverse Event Form of the CRF. Detailed information on the compilation of the Adverse Event Form is available in [Appendix 1](#).

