6.2.4 Severity

The Investigator must assess the severity of the event according to the following terms and assessments. The intensity of an event should not be confused with the term “serious” which is a regulatory definition based on patient/event outcome criteria.

Mild: Some discomfort noted but without disruption of daily life

Moderate: Discomfort enough to affect/reduce normal activity

Severe: Complete inability to perform daily activities and lead a normal life

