6.4 NOTIFICATION AND REPORTING OF SERIOUS ADVERSE EVENTS

6.4.1 Serious Adverse Event (SAEs)

That are considered to be ‘related’ and ‘unexpected’ are to be reported to the Sponsor within 24 hours of learning of the event and to the Main REC within 15 days in line with the required timeframe. For further guidance on this matter, please refer to Appendix 2

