6.7 PROCEDURES FOR REPORTING BLINDED ‘UNEXPECTED’ AND RELATED’ SAES

In the case of a blinded study, it is recommended the treatment code for the patient is broken in the reporting of an ‘unexpected and related’ SAE. However, the blind should be maintained, where possible and appropriate, for staff that are involved in data analysis and interpretation. It is the allocated responsibility of the CI by the

Sponsor for vigilance management and reporting. In this instance, an allocated unblinded individual (s), with no involvement in data management of the study should be responsible for the unblinding event. The unblinding of single cases by the PI/CI in the course of a clinical trial should only be performed if necessary for the safety of the trial subject.

It is recommended that in the case of a blinded study, the case is assessed for seriousness, expectedness and causal relationship as if it was study procedures that caused the reaction. If the case appears to be an ‘unexpected and related’ SAE then it should be unblinded and should be reported to the appropriate Main Research Ethics Committee within the required timelines outlined in section. For further guidance on this matter, please refer to [Appendix 1](#).

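### Causality of adverse events is to be judged against a trial treatment that the protocol says does not exist; the research procedures that could cause harm are not named as the reference

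*Protocol*

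**What the plan says.** Section 6.2.2 sets the rule for serious adverse events: "The Investigator must assess the causality of all serious adverse events in relation to the trial treatment according to the definition given". Section 6.1.1 sets the rule for every adverse event: the Principal Investigator is to "make a causality assessment of the treatment using one of the four given definitions: certainly related, probably related, possibly related and definitely unrelated".

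Section 6.0, which opens the same part of the protocol, says of pharmacovigilance: "Not applicable to current protocol has no treatment or therapy is a consequence of planned actions". Section 4.4 also states that the protocol requires no additional treatments.

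The relatedness rating has a consequence. Section 6.2.3 makes an unexpected and related serious event a matter for immediate reporting. Section 6.4.1 sets the deadlines for such events: "That are considered to be ‘related’ and ‘unexpected’ are to be reported to the Sponsor within 24 hours", and to the Main REC within 15 days.

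One section uses a different reference. Section 6.7, on blinded studies, recommends that "the case is assessed for seriousness, expectedness and causal relationship as if it was study procedures that caused the reaction".

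**The concern.** A causality rating means something only if the assessor knows which exposure is under suspicion. Here the named exposure is absent by the protocol's own account, while the exposures that do exist are not named. An assessor who follows the wording exactly has nothing to relate the event to.

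At stake is the sorting of events that the research itself may have caused, such as a complication of a venepuncture done only for BBR, or of tissue taken for research. These are the events that the related-and-unexpected route is meant to pick out. If the reference is wrong, some may be filed as unrelated, and relatedness ratings pooled over assessors would not mean the same thing from one record to the next. The protocol now extends recruitment to all specialties and to patients without capacity, so more assessors will have to apply this wording.

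**Working it through.** No arithmetic applies. The check sets the sections side by side.

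| Question | Protocol section | Answer |
|---|---|---|
| Causality against what? | 6.1.1 | The treatment |
| | 6.2.2 | The trial treatment |
| Is there a treatment? | 6.0 | No |
| | 4.4 | No additional treatments required |
| What does the research do to participants? | 4.4 | Up to 50 ml of blood per occasion, with an extra venepuncture if no clinical one is scheduled; saliva, swabs, urine, faeces; tissue taken at surgery |
| | 1.1 (Patient Pathways) | Up to 10 minutes added to non-radiation clinical assessments such as MRI or ultrasound |
| | 1.4 | Non-invasive monitoring devices |
| Are these the causality reference anywhere? | 6.7 | Yes, as study procedures, but only for a blinded study |
| Is this study blinded? | 4.3, 4.8 | No: randomisation and unblinding are both marked not applicable |
| What depends on relatedness? | 6.2.3, 6.4.1 | Immediate reporting; Sponsor in 24 hours, REC in 15 days |
| What does not depend on it? | 6.1.2, 8.6.2 | Serious events to the Sponsor in 24 hours (6.1.2) and to the REC in 72 hours (both) |

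A worked case shows the effect. Suppose a participant with no clinical venepuncture scheduled has one for BBR under 4.4, and a vessel injury leads to admission. Hospitalisation makes it serious under 6.1.2.

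1. Assessor A applies 6.2.2 as written. There is no trial treatment, so the event cannot be due to it, and the rating is the last of the four levels. The event does not enter the 6.4.1 route.
2. Assessor B takes the treatment to mean the intervention in the adverse-event definition of 6.1.1, counts the venepuncture as that intervention, and rates the event at or near the top of the scale. If it is also unexpected, it enters the 6.4.1 route.

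The same event can therefore land at opposite ends of the scale, and each assessor can point to protocol text. Under 6.1.2 and 8.6.2 both should still report it as a serious event. What differs is whether it is recorded as caused by the research and handled as such.

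**The case against.** The strongest reply has four parts.

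- **The definition is wider than a drug.** Section 6.1.1 defines an adverse event in someone given a pharmaceutical product or an intervention, and calls that the treatment. A research venepuncture can be read as an intervention. This stands as a possible reading, and it is why a rating of related is not ruled out. It is not the natural reading, since the same definition goes on to explain treatment by investigational agents, comparators and placebo, and 6.2.2 narrows it to the trial treatment.
- **Section 6.7 shows what is meant.** It does suggest the intention, but it is confined to a situation that cannot arise here.
- **Serious events are reported anyway.** Sections 6.1.2 and 8.6.2, and the serious-event row of the Appendix 1 table, carry no relatedness condition. This stands and limits the consequence. It does not correct the causality rating, and 6.4.1 describes a narrower route with a different REC deadline, so the reader cannot be sure which one governs.
- **The section is declared not applicable, and detail sits elsewhere.** Section 5.2 refers to standard operating procedures that cover adverse events around sampling, and 8.2 lists a serious-event reporting plan. Neither is available here, and they may name the right reference. But 6.1.1 and 6.2.2 are worded as obligations, so a protocol that both switches the section off and imposes duties under it still needs reconciling.

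**Conclusion.** The point holds in a limited form. The protocol requires causality to be assessed against an exposure that it says does not exist, and does not name the research procedures in its place. Harm from a research procedure may be rated unrelated or rated inconsistently, and so miss the related-and-unexpected route. This is a defect of safety classification. It changes no objective, analysis or sample size, and the protocol gives no event rate from which to estimate how many events are affected. The conclusion assumes that assessors work from the protocol text rather than from a procedure document that corrects it.

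Several stronger readings are tempting, and the documents do not support them:

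- *That procedure harm cannot be classed as related, or will go unreported.* The word intervention in 6.1.1 leaves room to class it as related, and 6.1.2 and 8.6.2 ask for serious events whatever their cause.
- *That the scale is defective because it has no level for an unlikely link, or no cut-off for related.* The levels are "certainly related, probably related, possibly related and definitely unrelated". Three carry the word related and one does not, so the division can be read from the labels. A further level is a matter of preference, and its absence could push doubtful events up as easily as down.
- *That the severity grades undermine reporting because ventilated patients already meet the worst one.* Severity does not decide any reporting route in 6.1.2, 6.2.3 or 6.4.1.
- *That an annual number of misrated events can be had by applying a serious-event rate to the more than 23,400 recruited.* No rate is given, that figure is cumulative recruitment, and most serious events would have nothing to do with a research procedure.

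**What to change.** In sections 6.1.1 and 6.2.2, replace the references to treatment and trial treatment with: a BBR research procedure (research blood draw or venepuncture, swab, research tissue sampling, added scan time, monitoring device). Then reconcile the surrounding text. Section 6.0 should say that no treatment is given but that adverse events are assessed against research procedures, and the study-procedure reference now found only in 6.7 should apply to this unblinded study. The adverse-event form should carry the same wording.

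The cost is a protocol wording change and a form update. A few more events may be classed as related, which is the purpose of the change. Patient management is not altered.

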6.2.3 Expectedness

The investigator must assess the expectedness of all SAEs according to the definition given. If the SAE is unexpected and related, then it needs immediate reporting.

6.2.4 Severity

The Investigator must assess the severity of the event according to the following terms and assessments. The intensity of an event should not be confused with the term “serious” which is a regulatory definition based on patient/event outcome criteria.

Mild: Some discomfort noted but without disruption of daily life

Moderate: Discomfort enough to affect/reduce normal activity

Severe: Complete inability to perform daily activities and lead a normal life

6.3 NOTIFICATION AND REPORTING ADVERSE EVENTS OR REACTIONS

If the AE is not defined as SERIOUS, the AE is recorded in the study file and the participant is followed up by the research team. The AE is documented in the BRC database, participants’ medical notes (where appropriate) and the CRF (where appropriate).

6.4 NOTIFICATION AND REPORTING OF SERIOUS ADVERSE EVENTS

6.4.1 Serious Adverse Event (SAEs)

That are considered to be ‘related’ and ‘unexpected’ are to be reported to the Sponsor within 24 hours of learning of the event and to the Main REC within 15 days in line with the required timeframe. For further guidance on this matter, please refer to Appendix 2

6.5 URGENT SAFETY MEASURES

The CI may take urgent safety measures to ensure the safety and protection of the clinical trial subjects from any immediate hazard to their health and safety, in accordance with Regulation 30. The measures should be taken immediately. In this instance, the approval of the Licensing Authority Approval prior to implementing these safety measures is not required. However, it is the responsibility of the CI to inform the

Sponsor and Main Research Ethics Committee (via telephone) of this event immediately.

The CI has an obligation to inform both the Main Ethics Committee in writing within 3 days, in the form of a substantial amendment. The Sponsor (JRO) must be sent a copy of the correspondence with regards to this matter. For further guidance on this matter, please refer to ([Appendix 1](#)).

6.6 ANNUAL PROGRESS AND SAFETY REPORTING

The CI will send the Annual Progress Report to the main REC using the NRES template (the anniversary date is the date on the MREC “favourable opinion” letter from the MREC) and to the Sponsor.

6.7 PROCEDURES FOR REPORTING BLINDED ‘UNEXPECTED’ AND RELATED’ SAES

In the case of a blinded study, it is recommended the treatment code for the patient is broken in the reporting of an ‘unexpected and related’ SAE. However, the blind should be maintained, where possible and appropriate, for staff that are involved in data analysis and interpretation. It is the allocated responsibility of the CI by the

Sponsor for vigilance management and reporting. In this instance, an allocated unblinded individual (s), with no involvement in data management of the study should be responsible for the unblinding event. The unblinding of single cases by the PI/CI in the course of a clinical trial should only be performed if necessary for the safety of the trial subject.

It is recommended that in the case of a blinded study, the case is assessed for seriousness, expectedness and causal relationship as if it was study procedures that caused the reaction. If the case appears to be an ‘unexpected and related’ SAE then it should be unblinded and should be reported to the appropriate Main Research Ethics Committee within the required timelines outlined in section. For further guidance on this matter, please refer to [Appendix 1](#).

6.8 OVERVIEW OF THE SAFETY REPORTING PROCESS/VILIGANCE RESPONSIBILITIES

The CI/PI has the overall vigilance oversight responsibility. The CI/PI has a duty to ensure that vigilance monitoring and reporting is conducted in accordance with the Sponsor’s requirements.

7.0 STATISTICAL CONSIDERATIONS

The data derived from the BRC Bioinformatics systems will not be analysed in isolation, but will form a core resource for Teaching, Research and Service development activities.

As such as formal statistical plan is not appropriate or required. All of the Investigators are experienced in medical statistics and clinical research.

7.1 PRIMARY ENDPOINT EFFICACY ANALYSIS

See above.

7.2. SECONDARY ENDPOINT EFFICACY ANALYSIS

See above.

7.3 SAFETY ENDPOINTS

Not applicable.

7.4 SAMPLE SIZE

Initial PILOT:

We aimed to approach most patients attending a CMR scan at Barts Health NHS Trust during the three month recruitment period. This was likely to be 600-1000 patients.

EXTENDED STUDY:

We aim to recruit as many patients as possible and as human and related resources allow (for consenting).

7.5 STATISTICAL ANALYSIS

See 7.0

8.0 DATA HANDLING & RECORD KEEPING

The conduct of the study will be monitored by the Investigators, and if required by a representative of the Sponsor in accordance with the GCP Guidelines. The investigator will co-operate fully with any study monitors and auditors.

The organisation, monitoring, and quality assurance of the present clinical study is the responsibility of the Sponsor.

In order to ensure the accuracy of data, direct access to source documents by the representatives of both the Sponsor is mandatory. Anonymity of the subject will be maintained at all times.

8.1 CONFIDENTIALITY

The Investigator has a responsibility to ensure that patient anonymity is protected and maintained. They must also ensure that their identities are protected from any unauthorised parties. Information with regards to study patients will be kept confidential and managed in accordance with the eight core principals of the Data Protection Act (2018), NHS Caldicott Guardian provisions, The Research Governance Framework for Health and Social Care (Second Edition 2005), NRES Research Ethics Committee Approval and the regulations of the Barts Health NHS Trust.

Subjects will be informed that their data are held on file, that these data may be viewed by Sponsor on behalf of the Sponsor and by external auditors on behalf of either the Sponsor or regulatory agencies. They will similarly be informed that this data and a report of the study will be submitted to the Sponsor and may also be submitted to government agencies and perhaps for publication, but that they will only be identified in such reports by their study identification number, initials and perhaps their gender and age. The investigators undertake to hold all personal information in confidence.

8.2 STUDY DOCUMENTS

- A signed protocol and any subsequent amendments
- Sponsor Self-Monitoring template for the trial team to complete on a regular basis as detailed by the Monitoring section
- Current/superseded Patient Information Sheets (as applicable)
- Current/superseded Consent Forms (as applicable)
- Indemnity documentation from Sponsor
- Conditions of Sponsorship from Sponsor
- Conditional/final R&D Approval
- Signed site agreement
- Ethics submissions/approvals/correspondence
- CVs of CI and site staff
- Delegation logs
- Staff training logs
- Site signature logs
- Patient identification logs

- Screening logs
- Enrolment logs
- Protocol training logs
- Correspondence relating to the study
- Communication Plan between the CI/PI and members of the study team
- SAE reporting plan for the study

8.3 CASE REPORT FORM

Presentation of the CRF

The CRF to be used for the study consists of pages that contain within the header or footer the Protocol number, subject initials, subject number and other relevant information. It is composed of an introductory section for the selection and inclusion of subjects in the study and a section for the treatment period. Contained within the treatment period section are the forms for registration of possible adverse events and for any suspension of the study.

How to use the CRF

All CRFs will be completed using a ball-point pen with black ink. All unused CRFs for drop-outs must be retained.

All requested information must be entered on the CRFs. If an item is not available or is not applicable, this fact should be indicated; there should be no blank spaces. Corrections should be made by striking through the incorrect entry with a single line and by entering the correct information adjacent to it. The correction must be initialled and dated by an Investigator or a designated qualified individual. Each set of completed CRFs must be reviewed, signed and dated by an Investigator. The completed original CRFs are to be returned to the Sponsor as soon as is practicable after completion and review. A photocopy of each completed CRF is to be retained by the Investigator.

